All participants will complete brief daily surveys for two weeks: one week pre- and one week post-quit date.. Participants will receive a daily text and/or email containing a link for the daily survey and will be able to complete the survey via internet on a smartphone, tablet or computer. Prior research from our group indicates 2 weeks of daily surveys is feasible with good retention (95%).¹³³ Participants will report CC smoking, EC use, NRT use (groups A and B only), text message utilization, nicotine dependence, quit attempts, and adverse events on daily surveys (Table 2). At the conclusion of the 12-week treatment period, participants will complete an end of treatment survey to report CC smoking or EC use and withdrawal symptoms. Those still smoking will also report motivation to quit, nicotine dependence, and self-efficacy to quit. In addition, participants will be encouraged but not required to submit another breath CO sample using their CoVita iCO device. The primary outcome for this RCT is CO confirmed 7-day point-prevalence abstinence from CCs at the end of treatment (i.e., at the 3-month follow-up). Per the Society for Research on Nicotine and Tobacco (SRNT) report on biochemical verification,¹³⁴ we will use CO of < 6 parts per million (ppm) as the cutoff for confirming CC abstinence. We will not contact participants for the 12 weeks following the treatment period. All participants will then complete a 6-month follow-up survey (i.e., 24 weeks after the baseline assessment) to report any CC smoking or EC use and withdrawal symptoms. Those who relapsed or continued to smoke CCs will also report motivation to quit, nicotine dependence, and self-efficacy to quit. In addition, all participants will be encouraged but not required to submit a final breath CO sample using their CoVita iCO device.

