All participants will receive daily text message support throughout the 12-week treatment period. We will use texts from SmokefreeTXT, a free interactive text message cessation service provided by Smokefree.gov that has been used with young adult smokers,¹⁴³ uses empirically validated Behavior Change Techniques,^{144,145} and has been employed to support engagement in prior smoking cessation research.¹⁴⁶⁻¹⁵⁰ Data from our ongoing research indicate young adult smokers generally find daily text messages to be helpful and acceptable. For example, in open-ended feedback participants reported that daily text messages about smoking cessation "...made me realize that there's a way to cope," "...felt like I had someone there to help," "...reminded me of my goal to stop smoking," and "...[were] very helpful!" We will use qualitative and survey data from [name] COBRE-funded research to modify messages from SmokefreeTXT to optimize appeal and engagement for young adult dual users in the proposed RCT. In addition, we will modify text messages according to participants' assigned group. For example, text messages for participants in groups A and B will encourage regular use of NRT throughout the study period. Text messages for groups B and D will support CC and EC cessation while messages for groups A and C will support CC cessation and EC continuation. The text message service will be interactive for all participants. In addition to receiving daily texts, participants will have the opportunity to send text messages to our service which will prompt automatic responses. For example, a participant who texts "help" will receive a pre-programmed text message response containing suggestions for coping with urges to smoke cigarettes. We will work with ICF incorporated, the provider for National Cancer Institute's SmokefreeTXT platform, to deliver all daily text messages and to deliver links to daily surveys.

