All participants will have the option to refer others to participate in the study and will receive \$25 compensation for each person that they refer who completes a baseline survey. Participants will have the opportunity to refer a maximum of 5 participants. During the ID check Zoom call, we will ask all new participants whether they were referred from someone currently enrolled in the trial. If they were, we will ask them to provide the name of the person that referred them. After the ID check Zoom call, the research assistant will look up the referral source in our REDCap database and provide a \$25 gift card and payment acknowledgment to the referral source if the individual who was referred completes the baseline survey.

Retention

We will employ a series of strategies to retain participants for the entirety of this 6-month study:

- 1) Proximal compensation for survey completion. Participants will receive electronic gift cards soon after completing each of the study surveys.
- 2) Personalized reminders to complete study surveys. All participants will receive reminders to complete any missed weekly, baseline, 3-month or 6-month surveys.
- 3) Personalized thank you messages in response to completing surveys. We will send emails following the completion of the baseline and 3-month surveys to thank participants and encourage continued participation.

All participants will have the opportunity to earn up to \$493 in gift cards for participating in this 6-month study. The table below outlines compensation for each study activity:

Study activity	Compensation
Initial call and ID verification	\$15 total
Baseline survey	\$30 total
Viewing short informational video	\$10 total
2 weeks of daily questionnaires	\$2 per log entry for a total of \$28
Week 1 + 2 surveys (\$10 each)	\$20 total
Week 3 + 4 surveys (\$15 each)	\$30 total
Week 5 + 6 surveys (\$20 each)	\$40 total
Week 7 + 8 surveys (\$25 each)	\$50 total
Week 9 + 10 surveys \$30 each)	\$60 total
Week 11 survey (\$35)	\$35 total
3 month and 6 month surveys	\$50 each for a total of \$100
Bonus for providing breath samples on baseline survey, weekly surveys, and 3-month and 6-month follow-up surveys	\$5 per bonus for a total of \$70
Total possible compensation	\$493

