For research involving survey, questionnaires, etc.: Describe the setting and the mode of administering the instrument and the provisions for maintaining privacy and confidentiality. Include the duration, intervals of administration, and overall length of participation.

	Not applicable
--	-----------------------

All surveys and questionnaires will be administered remotely via the University of Vermont College of Medicine's REDCap account, which is a secure, HIPAA-compliant platform. We will text participants links to their daily questionnaires during weeks 2 and 3 of the study. We will email participants secure links to their baseline, weekly, 3-month, and 6-month surveys. We will mail all participants a personal iCO Smokerlyzer device (<https://www.bedfont.com/ico>). We will instruct participants to download the Smokerlyzer iCOquit application on their smartphone or tablet. Participants will use their email address to create an account and access the app and complete the CO testing at their baseline, weekly, 3-month, and 6-month surveys. At each survey, participants will be encouraged but not required to submit a breath sample using their device and the Smokerlyzer iCOquit app on their cell phone or tablet. De-identified breath CO results will be stored in coVita's iCOquit app database for the duration of the study. Participants will also manually enter their results into the appropriate REDCap survey. Research personnel will access the breath CO data through email and will download the data to the University of Vermont College of Medicine secure drive. Results from the Smokerlyzer iCOquit application will be securely coded with the participants' unique ID and securely stored with other participant data.

The daily surveys during weeks 2 and 3 of the treatment period will be completed on the college of medicine's secure REDCap platform. Links to the REDCap daily survey will be sent via text message as part of the text message support administered by ICF Inc. Participants will be required to enter their participant ID into the daily survey to complete each daily survey.

TYPES OF PROCEDURES (Please do not use the "other" option unless the procedure is not listed.)

Check all that apply.

	Survey (mail, telephone, in-person, on-line)		Blood drawing:		Vol. _____		Over days, weeks?		Type & Amt.

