All study data will be confidential and accessible only by IRB-approved study personnel. All study data will be downloaded directly into the password-protected study database and stored on the University of Vermont College of Medicine's secure server. Each participant will be assigned a unique identification code (ID) to maintain confidentiality. Participants' names, contact information (telephone number and e-mail address), informed consent documents, and payment form and a document describing each participant's ID number will be kept in a secure file on the University of Vermont College of Medicine's secure server. Participation will entail a text message intervention. Thus, we will ask participants to text a third party vendor (ICF Incorporated's SmokefreeTXT) to initiate the text message support services. In addition, participants will be asked to share their email address with Rybbon, a third party vendor that we will use to distribute digital gift cards as compensation for participating. During the consent process, we will inform all potential participants that, if they decide to participate, we will ask them to enroll in our study text message services, which will require sharing their phone number with ICF Incorporated and we will ask them to share their email address with Rybbon to receive compensation. Participants' contact information will remain confidential and will not be accessible by anyone other than those previously described. All research personnel will receive training in confidentiality.

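### Daily survey links are sent through the text-message treatment that participants must start themselves, so daily data around the quit date can go missing in step with engagement; Assessments conflicts on the route

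*Combined protocol and SAP*

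**What the plan says.** The section on administering surveys and questionnaires names text as the route for the daily surveys: "Links to the REDCap daily survey will be sent via text message as part of the text message support administered by ICF Inc". The same section has the baseline, weekly, 3-month and 6-month links e-mailed. The Treatment section gives the vendor both tasks: "to deliver all daily text messages and to deliver links to daily surveys".

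The Treatment section also says "All participants will receive daily text message support throughout the 12-week treatment period". Under Protection against Risk, however, the service starts with an act of the participant: "we will ask participants to text a third party vendor (ICF Incorporated's SmokefreeTXT) to initiate the text message support services".

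Assessments gives a different rule for the daily link: "Participants will receive a daily text and/or email containing a link for the daily survey".

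The Retention section lists the surveys that get reminders, and the daily ones are not among them: "All participants will receive reminders to complete any missed weekly, baseline, 3-month or 6-month surveys".

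The daily entry is linked to a person by hand: "Participants will be required to enter their participant ID into the daily survey to complete each daily survey".

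According to Assessments and Table 2, the daily surveys ask about smoking, EC use, NRT use, text use, dependence, quit attempts and adverse events, for one week before and one week after the quit date.

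**The concern.** A measurement instrument is delivered through a treatment. All four groups get texts, but the content differs by group: groups A and C are encouraged to continue ECs, groups B and D to quit them. If the survey link arrives only inside that stream, a participant who does not start it cannot answer, and non-response on the daily surveys follows engagement with the assigned messages. Engagement could differ between the EC strategies, which are the arms that Aims 2 and 3 compare.

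At stake is the day-level record around the quit date and, depending on how the count is defined, one of the two Aim 3 comparisons: the total number of study-related adverse events reported during treatment. A count of reports depends on how often people are asked. The strategy with more unconnected participants would be asked less often and could look safer for that reason alone.

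The typed ID is a second, smaller weakness in the same procedure. A mistyped ID can leave an entry unmatched. It can also file the entry under another participant if it happens to be a valid ID.

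**Working it through.** **Inputs from the protocol**
- Daily entries: the compensation table pays $2 per entry to a total of $28, so 28 / 2 = 14.
- Weekly surveys: the same table lists weeks 1 to 11, so 11. The 3-month survey closes treatment, so 1 more. As a check, the breath-sample bonus of $70 at $5 each is 70 / 5 = 14 samples, which equals baseline + 11 weekly + 3-month + 6-month.
- Randomised: 390.

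**Input not in the protocol**
- The share of participants not connected to the text service. It is assumed below, and so is any gap between EC strategies.

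**Entries at risk if text is the only route**
- Maximum daily entries: 390 x 14 = 5,460.
- With an assumed 5%, 10% or 20% never connected: 0.05 x 5,460 = 273; 0.10 x 5,460 = 546; 0.20 x 5,460 = 1,092.

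**Reporting occasions for adverse events during treatment, if daily reports are counted**
- Connected: 14 + 11 + 1 = 26. Not connected: 11 + 1 = 12.
- Share using the text channel: 14 / 26 = 54%.
- Mean occasions with a share o not connected: 26(1 - o) + 12o = 26 - 14o.
- o = 0.10: 24.6. o = 0.20: 23.2. o = 0.30: 21.8.
- 10% v 20%: 24.6 / 23.2 = 1.06. 10% v 30%: 24.6 / 21.8 = 1.13.
- Equal shares in both strategies: 1.00.

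**If only the weekly and end-of-treatment reports are counted**
- 12 occasions for everyone: 12 / 12 = 1.00, whatever the share not connected.

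These are ratios of occasions, not of events. One event may be reported several times or once only, so the ratio of reported events need not equal the ratio of occasions.

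**Typed IDs**
- Up to 5,460 manual entries. The protocol gives no error rate. Each assumed 1% of mistyped entries is about 55 records (0.01 x 5,460 = 54.6).

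**Delivery rules side by side**
- Treatment and the survey section: the vendor sends the daily link, and the survey section names text as its route.
- Assessments: text, e-mail or both.
- Protection against Risk: the participant starts the texts.
- Retention: no reminder for a missed daily survey.

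Only the Assessments wording leaves room for a participant without texts to get the link, and it does not promise everyone an e-mail.

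**The case against.** The strongest reply is that little is really lost. Table 2 also schedules EC use, NRT use, quit attempts and adverse effects on the weekly surveys, with cigarettes per day for those who relapsed or did not quit. Those surveys are e-mailed and have reminders. Adverse-event collection is described as weekly in several places, including the section on reporting AEs and SAEs. Eligibility requires a phone that can receive daily texts, staff review active participants every week, and other missing outcomes are to be multiply imputed. All of this stands, and it limits the loss to daily detail and reporting occasions. It does not remove the point. The weekly review mentions no check that the texts are active, and the plan does not say what enters the imputation model, so missingness driven by disengagement may not be captured.

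A reader might infer more than the documents support:
- That everyone without texts loses all quit-week data. Assessments permits e-mail, and the weekly surveys cover much of the same content.
- That leaving the texts also stops the links. This is plausible, but no section says what happens after someone leaves.
- That the daily surveys are the source for time to relapse, days of EC or NRT use, or the Aim 3 count. Statistical methods names no source, and surveys ending one week after the quit date could not alone supply 12 weeks of use or relapse.
- That the imbalance is larger because only weeks 2 and 3 matter. Aim 3 counts events over the whole treatment period.
- That Aim 2 loses power. Not starting the texts is non-adherence and would be the same however surveys were sent. Participants also get arm-specific written instructions and a video.

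**Conclusion.** The protocol gives conflicting delivery rules for the daily survey. The more specific one makes receipt depend on a treatment that the participant has to switch on. Under that rule, a participant who never starts the texts misses up to 14 daily entries; that the same holds for one who leaves them is an inference. The missing entries would be related to engagement and could differ by EC strategy. The documents do not show that they would differ.

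The size is modest and conditional. The ratio of mean reporting occasions is about 1.06 or 1.13 under the assumed gaps if daily adverse-event reports enter the Aim 3 count, and 1.00 if they do not. The CO-verified 3-month outcome is collected with an e-mailed survey and is not touched. The typed ID is an avoidable source of lost or misfiled records at an unknown rate; the ID format and any validation are not described. This is an inexpensive improvement, not a threat to the primary abstinence analysis.

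**What to change.** 1. Reconcile Assessments, Treatment and the survey-administration section on one rule: every participant gets the daily survey by direct REDCap e-mail, whether or not the text service is active. Keep the text link as an additional prompt.
2. Make the e-mailed links participant-specific, so that no ID has to be typed on that route.
3. Add the daily surveys to the reminders in the Retention section.
4. In Statistical methods, commit to reporting daily-survey missingness by arm and by text activation.

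The cost is protocol wording and REDCap set-up, using e-mail links already planned for the other surveys. Some participants will get two prompts on the same day. Days not recorded around the quit date cannot be recovered reliably later, so the change belongs before enrolment.

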Assessments. All assessments will be remote and accessible by smartphone, tablet, or computer. After confirming eligibility and consenting to participate, participants will be randomly assigned to one of the four study groups (Table 1) and study personnel will mail a welcome package including study information, a CoVita iCO personal smokerlyzer device, and NRT (for groups A and B only). Upon receipt of the welcome package, participants will complete a brief baseline survey on the internet (Table 2) and will be encouraged but not required to submit a baseline breath CO sample using the CoVita iCO device and iCOquit mobile application which is compatible with Mac iOS and Android operating systems for smartphones and tablets. We will not ask participants to return their personal CoVita iCO Smokerlyzer. All participants will be free to keep their personal CoVita iCO Smokerlyzer after the conclusion of their participation.

Table 2. Schedule of assessments

	Baseline	Daily 1 wk pre- and 1 wk post-quit	Weekly surveys and End of Tx	6-Month follow-up
Human subjects protocol form 1/25/2022				

Individual-level factors				
Socio-demographic information	x			
Tobacco use history & breath CO	x			
Motivation rulers for CC & EC cessation ¹²⁵	x		x ^a	x ^a
CC and EC dependence and demand				
CC Strong dependence questionnaire	x		x ^a	x ^a
EC Strong dependence questionnaire	x		x ^a	x ^a
Cigarette & e-Cigarette Purchase Tasks ¹²⁸	x		x ^a	x ^a
Minnesota Nicotine Withdrawal Scale ¹³¹	x		x	x
Intervention engagement & adverse effects				
Preference for quitting CCs only versus CCs + ECs simultaneously	x			
Frequency of EC use (groups A & C) or EC abstinence (groups B & D)		x	x	x
NRT use and perceived helpfulness (groups A & B)		x	x	
Responses to text messages and perceived helpfulness		x	x	
Study-related adverse effects		x	x	x
Outcomes				
Primary: CO-verified 7-day point prevalence CC abstinence			x	x
Secondary:				
CO-verified 30-day CC abstinence			x	x
Self-reported attempts to quit CCs		x	x	x
Cigarettes per day	x	x	x ^a	x ^a
Time to first CC after waking ¹³² and CC addiction ladder	x	x	x ^a	x ^a

^aAssessed only among participants who relapsed or failed to quit CCs. CC=Combustible cigarettes; EC=Electronic cigarette; NRT=Nicotine replacement therapy; Tx=Treatment.

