Treatment. The consent form explains that a primary aim of this RCT is to test whether quitting versus continuing ECs is more effective when quitting CCs, and currently there is mixed evidence supporting both strategies. After randomization, all participants will receive information about the study including instructions to set a quit date and which product(s) to quit. Written instructions for the intervention will be provided and participants will also be asked to view a supplementary video presentation. We will provide participants in groups A and C with instructions to quit CCs but continue using ECs with the rationale that ongoing use of ECs could help them abstain from CCs. Specifically, we will instruct participants in groups A and C to use ECs in place of CCs to help cope with cravings or urges to smoke CCs. In contrast, participants randomized to conditions B and D will receive instructions to quit CCs and quit ECs with the rationale that quitting ECs could help them abstain from CCs. We will instruct participants in groups B and D to abstain from vaping because ECs could trigger relapse to CCs. Participants in groups A and B will also receive instructions for how to use NRT.

Participants randomized to conditions A and B will be mailed 3 one-month supplies of dual 14 mg NRT patches and 4 mg mini-lozenge because this appears to be the most effective non-prescription medication combination for smoking cessation.¹⁴⁰ However, participants will have the option to stop receiving NRT from the study. Participants will be instructed to start using both forms of NRT 2 weeks prior to their quit date because pre-quit NRT appears to increase the effectiveness of NRT.¹⁴¹ Further, the recommended use for the NRT has recently been changed to incorporate use while smoking because "the FDA has determined that there are no significant concerns with using NRT products at the same time as another nicotine-containing product like a cigarette (<https://www.nicodermcq.com/faq.html>)."¹⁴² We will instruct participants to use one patch per day and use mini-lozenges when they have cravings to smoke CCs (condition A) or cravings to smoke CCs or use ECs (condition B), without surpassing 24 mini-lozenges in one 24-hour period. Anyone for whom NRT is contraindicated will be excluded from the proposed RCT. In addition, though risk of serious adverse events from NRT is low (eg.¹⁴²), we will assess adverse events related to study procedures on weekly surveys.

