Statistical methods. Baseline participant characteristics, including socio-demographic information and tobacco use history, will be compared between the four conditions using analyses of variance for continuous and chi-square tests for categorical variables. Differences between conditions at baseline will be considered as potential covariates in subsequent analyses. Consistent with the intent-to-treat approach,¹⁵² our primary analysis will include all randomized participants who complete the baseline survey, independent of early dropout. Participants who are missing abstinence data will be assumed to be smoking. Missing survey data on other outcomes will be imputed using multiple imputation.¹⁵³ For our Aim 1 primary outcome, we will compare the proportion of participants who achieved CO-verified (< 6 ppm) 7-day point-prevalence abstinence at the end of treatment between conditions that were provided NRT versus no NRT using logistic regression. For our Aim 2 primary outcome we will compare the proportion of participants who achieved CO-verified 7-day point-prevalence abstinence at the end of treatment between conditions assigned to quit CCs only versus quit CCs and Ecs simultaneously. For our Aim 3 primary outcome we will compare the conditions assigned to quit CCs only versus quit CCs and Ecs simultaneously on 1) the proportion of participants who report a serious study-related adverse event using a chi-square test and 2) the total number of reported study-related adverse events during the treatment period using a t-test or nonparametric test, depending on the distribution. In addition, we will conduct an exploratory analysis using logistic regression to examine the interaction between the treatment arms (NRT versus no NRT by continue EC versus quit EC) with CO-verified 7-day point-prevalence abstinence as the outcome. We will also examine the effect of EC continuation versus NRT on CC abstinence by comparing Group B (quit CCs and Ecs with NRT) versus Group C (quit CCs and continue Ecs without NRT) using logistic regression. We will conduct a series of sensitivity analyses using 30-day abstinence at the 6-month follow up as the outcome and test condition as a predictor of time to relapse after quit day using Cox proportional hazards regression survival analyses. Finally, we will conduct sensitivity analyses when missing data are treated as missing.

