Additional secondary analyses will explore moderators and intervention effects on relevant smoking outcomes. For example, we will test days of NRT use as a moderator of NRT's effect on abstinence using logistic regression. Similarly, we will test days of EC use as a moderator of the effect of being assigned to continue versus quit Ecs on CC abstinence using logistic regression. We will assess baseline preference for continuing versus quitting Ecs as a moderator of the effect of being assigned to continue versus quit Ecs on CC abstinence using logistic regression. Among participants who fail to quit CCs, we will examine condition as a predictor of change in amount of CC use, self-reported attempts to quit CCs, nicotine dependence, self-efficacy to quit CCs, and motivation to quit CCs. Analyses will be performed using SAS Statistical Software V9.4 (SAS Institute, Cary, NC). Statistical significance will be determined based on p<.05 for all analyses.

Sample size justification. We propose recruiting, consenting, and randomizing a sample of 390 participants. Given the high rate of fraudulent responses in remote studies, we anticipate that we will need to consent 1,030 individuals in order to verify the identification and randomize 390 participants. Based on prior remote tobacco treatment research among young adults,³³ we estimate 80% retention of randomized participants and thus anticipate retaining 312 participants by the end of treatment when we will assess our primary outcome. This proposed sample size is based on having sufficient power for detecting group differences on the primary outcome of 7-day point-prevalence abstinence at the end of treatment (i.e., week 12) for the treatment comparisons in Aims 1 and 2. A sample size of 78 in each of the 4 treatment groups will give over 90% power to detect a difference between NRT and No NRT and 80% to detect a difference between CC+CE and CC only in 7-day point-prevalence abstinence rates, assuming overall rates of 31% in the NRT and 12% in the No NRT group and overall rates of 15% in the CC+CE and 28% in the CC only group with $\alpha=.05$. While we know of no prior trials of NRT for young adults or smoking cessation treatment for dual users, these estimates are based on relevant prior trials of NRT or text messages for smoking cessation.^{37,69,140,154}

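### The intent-to-treat primary set leaves out randomised participants who skip a baseline survey taken after randomisation and after the arm-specific package arrives

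*Combined protocol and SAP*

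**What the plan says.** Statistical Considerations, Statistical methods, describes the approach as intent-to-treat and then defines the set: "our primary analysis will include all randomized participants who complete the baseline survey, independent of early dropout". For the outcome it adds: "Participants who are missing abstinence data will be assumed to be smoking". The only missing-data sensitivity analysis is the last one listed: "we will conduct sensitivity analyses when missing data are treated as missing".

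The order of events is under Procedures, Assessments. Eligible, consenting people are randomised and sent a package, which includes NRT only for groups A and B. Then: "Upon receipt of the welcome package, participants will complete a brief baseline survey on the internet". The Treatment paragraph says: "After randomization, all participants will receive information about the study including instructions to set a quit date and which product(s) to quit". It does not say whether that instruction reaches participants before or after the baseline survey.

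The Retention section plans for missed surveys: "All participants will receive reminders to complete any missed weekly, baseline, 3-month or 6-month surveys". The Sample size justification counts retention from randomisation: "we estimate 80% retention of randomized participants and thus anticipate retaining 312 participants by the end of treatment". It also places identity verification before randomisation, with 1,030 consented to randomise 390.

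**The concern.** An intent-to-treat set is fixed at randomisation. Here it is fixed later, by an action participants take once the contents of the package have shown them whether they receive NRT. For the EC factor, prior knowledge of the assignment is an inference, because the documents place the instruction after randomisation but do not order it against the survey.

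Nothing in the plan brings the excluded people back. Counting missing as smoking applies only inside the reduced set, and the sensitivity analysis moves further away from all randomised.

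If the no-NRT or quit-both margin loses more non-quitters, its observed abstinence rises and the effects in Hypotheses 1 and 2 are understated. If the NRT or continue-EC margin loses more, they are overstated.

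A smaller point has the same cause. Table 2 collects preference for quitting CCs only or both products at this survey, and the plan uses it as a baseline moderator of the EC assignment. If participants already know their instruction, the assignment could influence the moderator.

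**Working it through.** **Inputs from the Sample size justification.** 390 randomised and 312 retained (80%); 78 per cell, so 156 per factorial margin; Aim 1 rates 31% vs 12%; Aim 2 rates 28% vs 15%; α = 0.05. I assume a two-sided test and equal allocation, so 390/2 = 195 randomised per margin.

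**Test.** Two-proportion z test, with d the absolute difference and p̄ the pooled rate:

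- SE0 = √[p̄(1−p̄)(1/n1+1/n2)]
- SE1 = √[p1(1−p1)/n1 + p2(1−p2)/n2]
- rejection = Φ((d−1.96·SE0)/SE1) + Φ((−d−1.96·SE0)/SE1)

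**The plan's own figures.** For Aim 2 with 156 per margin: p̄ = 0.215, SE0 = 0.0465, SE1 = 0.0459, (0.13 − 0.0912)/0.0459 = 0.845, power 80.1%. Aim 1 gives 98.6%. Both agree with the stated 80% and over 90%, and are not in dispute. With all 195 per margin at the same rates, power is 88.1% (Aim 2) and 99.6% (Aim 1).

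**Effect of the exclusion.** No document gives a baseline completion rate, so the losses are assumed. Let L be the share of a margin removed. If everyone removed is a non-quitter, the observed rate is p/(1−L) and n = 195(1−L). If they quit at half their margin's rate, the observed rate is p(1−0.5L)/(1−L).

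Worked case, 5% lost in continue-EC and 15% in quit-both, all non-quitters:

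- rates 0.28/0.95 = 29.5% and 0.15/0.85 = 17.6%
- n = 185.25 and 165.75
- d = 0.118, SE0 = 0.0456, SE1 = 0.0447
- (0.1183 − 0.0894)/0.0447 = 0.647, power 74.1%

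**Aim 2** (5% lost in continue-EC; true difference 13.0 points):

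| Loss in quit-both | Observed difference, all non-quitters | Power, all non-quitters | Power, half-rate |
|---|---|---|---|
| 10% | 12.8 | 82.5% | 84.0% |
| 15% | 11.8 | 74.1% | 79.5% |
| 20% | 10.7 | 63.3% | 73.8% |

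**No true effect** (21.5% in both margins, the mean of the planning rates for either aim; 5% lost in one margin):

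| Loss in other margin | False difference, all non-quitters | Rejection, all non-quitters | Rejection, half-rate |
|---|---|---|---|
| 10% | 1.3 points | 5.9% | 5.2% |
| 15% | 2.7 points | 9.0% | 6.0% |
| 20% | 4.2 points | 14.9% | 7.6% |

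**Other cases, all non-quitters.**

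- Reverse direction for Aim 2 (10/15/20% lost in continue-EC, 5% in quit-both): the difference grows to 15.3, 17.2 or 19.2 points.
- Aim 1 with 5% lost in NRT and 10/15/20% in no-NRT: power 99.3%, 98.6% or 97.1%. With 0% vs 20% it is 94.6%.
- Equal 5% loss: no false difference under the null; Aim 2 difference 13.0/0.95 = 13.7 points, power 88.6%.

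**Check.** Simulation (200,000 runs, Wald logistic test) gives 82.5%, 74.2% and 63.3% for the all-non-quitter Aim 2 cases, and 5.8%, 8.9% and 14.8% for the corresponding null cases.

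**Scale.** People lost: 195 × (0.05 + 0.10), (0.05 + 0.15) and (0.05 + 0.20) = 29, 39 and 49, against the 390 − 312 = 78 losses the plan expects by week 12. The 20% case is an extreme.

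**The case against.** The strongest objection is that the larger figures come from scoring everyone lost as a non-quitter. That is the plan's coding rule, not evidence about outcomes. If those lost quit at the usual 21.5%, the planned set is unbiased. The all-randomised analysis, with no week-12 data on them, would then itself create false differences of 1.1, 2.2 or 3.2 points and rejection of 5.8%, 8.4% or 12.9%. Under the half-rate assumption the two sets perform about equally: 5.2/6.0/7.6% for the plan and 5.2/5.8/6.8% for all randomised. This arithmetic is right. It is limited by the fact that people who skip the baseline survey remain participants: the plan sends participants the 3-month survey and reminds them, so their outcome need not be missing. The possibility is also a reason to keep the completer analysis alongside.

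Three further points have weight. Knowledge of the arm before the survey is explicit only for NRT, where power hardly changes, while the material power loss is in Aim 2. The 5% vs 10% case still exceeds the plan's 80% target. Early loss may also be small, because participants pass a consent quiz and a paid ID call, are paid $30 or $35 (the two compensation tables differ) for the baseline survey, and receive reminders. These points limit the likely size; they do not make the set intent-to-treat. Fraud control does not justify the exclusion either, since identity is verified before randomisation.

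**Conclusion.** The concern holds: the primary set is wrong as written. It carries the intent-to-treat label but is conditioned on an act after randomisation, and no analysis of all 390 is planned. Size and direction cannot be determined from the documents. Under the assumed unequal losses, all non-quitters, Aim 2 power falls from 88.1% to between 82.5% and 63.3%, and the false-positive rate rises to between 5.9% and 14.9%. Under the half-rate assumption the ranges are 84.0% to 73.8% and 5.2% to 7.6%. These figures assume that the planning rates hold in all randomised. This should be fixed, with medium confidence that it would matter in practice.

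**What to change.** 1. Define the primary set for Aims 1 and 2 as all randomised participants, analysed as randomised, with missing abstinence counted as smoking.
2. Keep baseline-survey completers as a sensitivity analysis.
3. Report baseline-survey completion by arm.
4. Ask EC preference before allocation, in the screener or the ID call. The Recruitment section already keeps screener data of consenting participants in the research record.

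The cost is a sentence of analysis text, one count by arm and one survey item moved. No participants or contacts are added. People who never start enter the denominator, so observed abstinence rates will be slightly lower. If the planning rates hold only in the 80% retained and everyone else counts as smoking, the rates over 195 per margin are 0.8 × 31% = 24.8% vs 0.8 × 12% = 9.6% (Aim 1, power 98.0%) and 0.8 × 28% = 22.4% vs 0.8 × 15% = 12.0% (Aim 2, power 77.9%).
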